2 RESEARCH DESIGN AND METHODS

2.1 OVERVIEW

To test the feasibility of a clinical trial implementing I-CAT for people with first-episode schizophrenia, a small RCT with 40 individuals (20 assigned to I-CAT and 20 to TAU) will be conducted. The objective of this small RCT is to conduct a feasibility trial of the I-CAT approach in anticipation of a larger scale trial. To complete this object, we will conduct a study using a small RCT comparing I-CAT to TAU (i.e., supportive therapy). This will allow us to evaluate the feasibility of recruitment, randomization, retention, assessment procedures, and the training and implementation of the revised I-CAT manual in a real-world setting. Successful completion of this stage of treatment development will provide preliminary information on the possible impact of I-CAT on stress reactivity.

Justification and Feasibility - The proposed study will evaluate the outcomes of the I-CAT intervention in a real-world clinical setting to estimate effect sizes in preparation for a larger clinical trial. We will begin standardizing the intervention, refine the clinician training protocol, and a measure of fidelity. The goal is to establish estimates of effect size before moving forward with a large-scale RCT. We are confident that comparing I-CAT to an active treatment will establish an accurate estimate of effect size from our key outcome domains.

Sample Size Justification - We have chosen to collect data from a sample size of 40 subjects with 20 in

each group. Currently, OASIS has a census of 140 people and admits approximately 3-5 people per month. With approximately 2 years to recruit 40 subjects, we will have to recruit approximately two subjects per month. In a previous randomized treatment trial at OASIS, we recruited 45 people with schizophrenia in approximately 30 months, suggesting these recruitment goals are realistic. 48 We conducted a power analysis using the Optimal Design power software developed by Raudenbush. The results suggest that, with 20 subjects per group, $\alpha=.05$, and covariates that account for 40% of the variance, the study should have reasonable power ($B = .70$) to reliably detect treatment effect sizes of .65 or larger (although in this proposal, we have not designed the study with the anticipation that we will see effect sizes of this magnitude). We will compute effect sizes from these analyses and regard them as clinically meaningful if they exceed .20 for more distal outcomes and .30 for more proximal outcomes.

Research Design - We will randomly assign 40 subjects to either I-CAT or ($n=20$) or TAU ($n=20$) for up to nine-months of individual therapy sessions. Blinded raters will assess subjects at mid-treatment, post-treatment, and follow-up. A computer program, held by the data manager, will determine randomization; randomization sequences will not be known by anyone in advance. The data manager will then do the randomization. Subjects will be instructed not to discuss the type of therapy they are receiving with the blinded research assistants. Any violations to treatment blinding will be noted in the study log and possibly addressed in subsequent data analyses.

Biological Specimen Analyses - Our primary outcome measure is cortisol. Our preferred method of analyzing cortisol will be collecting saliva at 5 times points over 2.5 hours and performing analyses with the Salimetrics High Sensitivity assay.

Cardiovascular Measures - Cardiovascular monitoring will include measurement heart rate variability (HRV). At the baseline and post-treatment visits, HRV will be measured over a 5 minutes rest period (watching a 5-minute nature video) to obtain resting state HRV data, then over 5 minutes of paced breathing, and finally over an additional 5 minute rest period (watching a 5-minute nature video). HRV data will be collected using a FirstBeat Bodyguard 2 device, a wearable IBI monitoring and recording device. CardioEdit/CardioBatch Plus, and Kubios HRV Standard will be used to prepare, edit and analyze vagal activity, 99,100 in 5-minute epochs, indexed by respiratory sinus arrhythmia.

2.2 SUBJECTS

Study subjects will be primarily drawn from the OASIS clinic at UNC Hospitals. Once a person is referred to the study (or self refers), a study clinician will meet with the individual (and any other individuals that she/he indicates, such as a family member) and describe the study protocol, expectations of study participation and potential study risks and benefits. The study clinician will evaluate the subject's understanding, and will not proceed with consent unless the individual understands these elements. All study subjects will sign a written informed consent document approved by the UNC Institutional Review Board. To obtain an estimate of IQ and to rule out any individuals with possible mental retardation, we will administer the WASI, which is comprised of Matrix Reasoning, Vocabulary, Similarities, and the Block Design subtests. Additional demographic and clinical information that will be collected as self-report for possible use as covariates includes: age, sex, ancestry, education, parent education, substance use, current medications, duration of outpatient treatment, and date of initial SSD diagnosis.

2.2.1 INCLUSION CRITERIA

1. DSM-V diagnosis of a SSD (Schizophrenia, Schizoaffective Disorder, Brief Psychotic Disorder, Schizophreniform Disorder, and Unspecified Schizophrenia Spectrum and Other Psychotic Disorder)

2. Less than 8 years of antipsychotic and/or psychological treatment for psychosis
3. Between the ages of 18-35, both genders, and any ancestry
4. IQ>80. IQ will be assessed using the Wechsler Abbreviated Scale of Intelligence (WASI)
5. Does not meet current substance dependence criteria
6. No hospitalizations for psychiatric reasons in the last 3 months
7. Not actively practicing meditation (not taking a workshop or practicing meditation in the past year)
8. Clinically stable (no psychiatric medication changes within the past month and on medication regimen not anticipated to change during the next 6 months)
9. Willing and able to provide informed consent.

3 ASSESSMENT OF DATA

At this stage of treatment development, specific outcomes include:

1. Feasibility- Can I-CAT be delivered within this treatment setting?
 - a. Attrition rates
2. Tolerability- How well is I-CAT accepted by the subjects?
 - a. I-CAT feedback survey outcomes
3. Intervention adherence
 - a. Attendance rates, session fidelity ratings
4. Evaluation of I-CAT
 - a. Primary and secondary outcomes will be compared between I-CAT and TAU

3.1 OUTCOMES

The central hypothesis is that I-CAT will increase positive emotions, increase role functioning, and decrease stress reactivity as measured by self-report measures and salivary cortisol. Secondary hypotheses are that I-CAT will decrease psychiatric symptoms, increase mindfulness, and increase well-being as measured by self-report, clinical interview measures, and heart rate variability. Guided by strong preliminary data, this hypothesis will be tested via four specific aims:

1. To examine the feasibility of implementing I-CAT at a community mental health clinic
2. To examine the tolerability of I-CAT at a community mental health clinic
3. To examine I-CAT adherence through attrition and attendance rates
4. We will also examine the impact of I-CAT on primary outcomes (positive emotions, role functioning, stress reactivity), and secondary outcomes (psychiatric symptoms, mindfulness, well-being) compared with TAU.

We hypothesize that I-CAT will be associated with:

- Improved primary outcomes including increased positive emotions, increased role functioning, and decreased stress reactivity at mid-point, post-test, and three-month follow-up.

- Improved secondary outcomes including decreased psychiatric symptoms, increased mindfulness, and increased well-being at mid-point, post-test, and three-month follow-up.

4 STUDY DESIGN

During this phase of the trial, 40 subjects will be assigned to one of two interventions (i.e., I-CAT or TAU) of 20 subjects each. Intervention will last for approximately 9 months. Subjects will be asked to complete a total of five in-person assessments at screening, baseline, mid-point, post-test, and three-month follow-up.

4.1 INTERVENTION

After subjects are randomized to treatment intervention (i.e., I-CAT or TAU), subjects will meet weekly for individual therapy sessions with master's level clinicians or advanced graduate students with at least a master's degree. Clinicians will be monitored by three experienced clinicians/ instructors with over 15 years of experience in the field ([name], [name], and [name]). Clinicians will also have weekly supervision. Sessions will be recorded and assessed with the fidelity scale.

4.1.1 I-CAT

I-CAT is a manual-based intervention (manual available upon request). Sessions include collaborative agenda setting, practice of skills, refining and problem-solving obstacles, and collaborative homework assignments.

Part I of I-CAT includes psychoeducation on stress reactivity and mindfulness and assessment of stressors. Part II of I-CAT integrates practice of mindfulness (e.g., sitting meditation, body scan) and positive coping strategies (e.g., identification of personal strengths, setting positive goals, active/constructive responding). Sessions focus on a new strategy broken down into small steps demonstrated and practiced in session. Handouts are provided to increase integration of new skills in daily routines and track practice of skills between sessions. Part III of I-CAT focuses on 1) development of an individualized daily routine integrating mindfulness and meaningful coping skills, and 2) development of positive and personally meaningful goals (e.g., return to school). Handouts are also utilized in Part III to break goals into small steps, track progress, and identify barriers to goal achievement.

I-CAT can be flexibly administered with a minimum of 14 sessions recommended to cover all skills and participate in the individualized plan, or up to 24 sessions based on client needs over a nine-month period. Subjects in the I-CAT condition will also complete coordinated specialty care appointments (e.g., medication management, family therapy, supported employment, peer support).

4.1.2 TAU

Subjects randomized to TAU participated in weekly or bi-weekly therapy sessions and coordinated specialty care appointments. Therapists conducting TAU sessions were instructed to conduct sessions as usual and to refrain from introducing I-CAT elements (e.g., mindfulness and positive psychology). The frequency and duration of TAU will be the same as I-CAT with subjects encouraged to complete at least 14 sessions over nine months.

4.2 STUDY PROCEDURES AND MEASUREMENTS

4.2.1 SCREENING VISIT

The following measures will be examined at screening:

- Demographics- We will collect information on age, sex, ancestry, education, parent education, smoking, substance use, current medications, duration of outpatient treatment, and date of initial SSD diagnosis.
- Intelligence- In adherence with our inclusion criteria that subjects must have an IQ greater than 80, the Wechsler Abbreviated Scale of Intelligence (WASI) will be administered.
- Diagnosis-The Structured Clinical Interview for the DSM-V (SCID) will be utilized to assess symptoms. The SCID is a semi-structured interview that assesses for DSM diagnoses. The SCID will be used to verify that subjects have a schizophrenia spectrum diagnosis before they are enrolled in the study. Raters will be trained to conduct the SCID to a gold standard of reliability (i.e., intraclass correlation > .80).

4.2.2 Baseline and Post-Treatment Visits

The following measures will be examined at the baseline and post-treatment visits:

- Daily Stress Inventory (DSI) - The Daily Stress Inventory (DSI; Brantley et al., 1987) is a 58-item self-report measure assessing the frequency and intensity of stressful events within the past 24-hours. If an event is endorsed, participants rate the amount of stress the event caused (0 = *did not occur*, 1 = *occurred but was not stressful* to 7 = *occurred and caused me to panic*). The DSI yields three scores: frequency (number of events endorsed as occurred; range 0 - 58), sum (sum of the total impact rating of endorsed events; range 0 - 406), average impact rating (AIR; average impact of ratings given items endorsed [sum/frequency]).
- Five Facets of Mindfulness (FFMQ) - The Five Facet Mindfulness Questionnaire (FFMQ; Baer et al., 2006) is a 39-item self-report measure assessing facets of being mindful in daily life (i.e., observing, describing, acting with awareness, non-reactivity to inner experience, and non-judging of inner experience). Items are endorsed on a five-point scale (1 = *never or rarely true* to 5 = *very often or always true*) and averaged for a total score and five subscale scores for each facet of mindfulness (range 1-5).
- Modified Differential Emotions Scale (mDES) - The modified self-report Differential Emotion Scale (mDES; Fredrickson et al., 2003) assessed the frequency of experiencing discrete emotions from the previous week. Items are endorsed on a five-point scale (0 = *not at all*, 4 = *most of the time*) and averaged to yield positive and negative emotion subscales (range for both 0-4).
- Perceived Well Being (PWB) - The Psychological Well-Being Scale (PWB; Ryff, 1989) is a 54-item self-report measure with items endorsed on a seven-point scale (1 = *strongly disagree* to 6 = *strongly agree*). Items are summed for a total score (range 54 - 324) and six subscale scores (i.e., autonomy, environmental mastery, personal growth, positive relations with others, purpose in life, self-acceptance; range 9 - 54).
- Short Self Compassion Scale (short SCS) - The Self-Compassion Scale Short Form (SCS; Raes et al., 2011) is a 12-item self-report measure of self-compassion. SCS items are endorsed on a five-point scale (1 = *almost never* to 5 = *almost always*) and are summed for a total score (range 12 - 60) and six subscales (i.e., self-kindness, self-judgment, common humanity, isolation, mindfulness, and over-identified; range 2 - 10).

- First Episode Social Functioning Scale (FESFS) - The First Episode Social Functioning Scale (FESFS; Lecomte et al., 2014) is a 42-item self-report measure assessing social functioning in early SSD. The FESFS includes a total score and eight subscales assessing: independent living skills, interacting with people in different contexts, social activities, intimacy, friendships, family relations, work, and school. Domain scores are averaged with higher scores reflecting better perceived functioning (range 0-4).
- Perceived Stress Scale (PSS) - The Perceived Stress Scale (PSS; Cohen et al., 1983) is a ten-item self-report measure of the degree to which daily situations from the past week are perceived as stressful, unpredictable, uncontrollable, as well as how “overloaded” individuals feel (0 = *never*, 4 = *very often*). Items are summed for a total score (range 0 – 40) with higher scores indicating more perceived stress.
- Positive and Negative Syndrome Scale (PANSS) - The Positive and Negative Syndrome Scale (PANSS; Kay et al., 1987) assessed current symptoms. PANSS items are rated on a seven-point scale with higher scores reflecting more severe symptoms (ICCs for study assessors >.90). Items are summed for a total score (range 30 – 210). Items were also averaged according to the five-factor structure with the most consensus across studies (Wallwork et al., 2012) to yield five subscales (range 1-7) assessing negative, positive, depression, excited, and disorganization symptoms.
- Abbreviated Quality of Life Scale (QLS) - The abbreviated Quality of Life Scale (QLS; Bilker et al., 2003) is a seven-item semi-structured interview assessing domains of functioning (i.e., intrapsychic foundation, interpersonal relationships, instrumental role, and engagement in community). Items are rated on a six-point scale yielding a sum total score (range 0 - 42) with higher ratings reflecting better functioning.
- Subjects will also provide saliva samples every half hour over 2.5 hours for collection of salivary cortisol
- Subjects will wear the FirstBeat Bodyguard 2 device to provide heart rate variability while resting and during a paced breathing activity.

4.2.3 Mid-Treatment and Three-Month Follow-up Visits

The following measures will be examined at the mid-treatment and three-month follow-up visits:

- Daily Stress Inventory (DSI)
- Five Facets of Mindfulness (FFMQ)
- Modified Differential Emotions Scale (mDES)
- Perceived Well Being (PWB)
- Short Self Compassion Scale (short SCS)
- First Episode Social Functioning Scale (FESFS)
- Perceived Stress Scale (PSS)
- Positive and Negative Syndrome Scale (PANSS)
- Abbreviated Quality of Life Scale (QLS)

5 STATISTICAL ANALYSES

5.1 DATA ANALYTIC PLAN

Feasibility will be defined by our ability to meet our recruitment targets (40 people), frequency of engagement in the intervention by participants (session attendance and attrition rates), and feedback on the intervention from I-CAT participants.

Differences between group demographics to check effectiveness of randomization will utilize independent samples t-tests (continuous variables) or Pearson chi-square tests (categorical variables). Little's Missing Completely at Random test will be performed to establish whether data is missing at random and to determine if data imputation will be needed for subsequent analyses.

To test whether intervention groups differ in their amount of change on treatment outcomes over time, data will be analyzed according to the intent-to-treat principle, in which all subjects randomized will be included in the analysis. To examine intervention effects on primary and secondary outcomes, linear mixed-effects models will be utilized with restricted maximum likelihood estimation where missing data will be handled via full information maximum likelihood. The linear mixed-effects models will include effects of time (i.e., baseline, mid-treatment, post-treatment, and follow-up), intervention group, and a group by intervention interaction with random intercepts to account for baseline differences on outcome variables. Observations classified as outliers (i.e., residual values less than or greater than 1% of all observations) will be excluded. Changes from baseline will be estimated using least-squares means for each intervention group.

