Efficacy Evaluations	
Primary outcome – Psychological - Least means change from baseline scores at mid-treatment, post-treatment, and follow-up on positive emotions (mDES), role functioning (QLS, FESFS), and stress reactivity (PSS, DSI).
 
Primary outcomes – Biological - Least means change from baseline to post-treatment on salivary cortisol.
 
Secondary outcomes- Psychological- Least means change from baseline scores at mid-treatment, post-treatment, and follow-up on psychiatric symptoms (PANSS), mindfulness (FFMQ, short SCS), and well-being (PWB).

	
Secondary outcomes- Biological- Least means change from baseline to post-treatment on resting/baseline heart rate variability (RSA).

Safety Evaluations	
A safety plan for the intervention sessions will be developed prior to the initiation of the study with [name], as well as the study clinicians.

Statistical and Analytic Plan	
Analyses will focus on average change over time (i.e., change from baseline scores) on primary outcomes (positive emotions, role functioning, stress reactivity, salivary cortisol) and secondary outcomes (psychiatric symptoms, mindfulness, well-being, heart rate variability). Analyses will utilize hierarchical linear models with random intercepts for each subject that will estimate the average change from baseline (i.e., least means change) for each treatment group (TAU, I-CAT) at mid-treatment, post-treatment, and follow-up timepoints.

DATA AND SAFETY MONITORING PLAN	
[name] will function as the Project Medical Officer. An independent physician will serve as the Medical Monitor ([name], from the Department of Psychiatry).

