5.2 POWER ANALYSIS

We conducted a power analysis using the Optimal Design power software developed by Raudenbush. The results suggest that, with 20 subjects per group, $\alpha = .05$, and covariates that account for 40% of the variance, the study should have reasonable power ($B = .70$) to reliably detect treatment effect sizes of .65 or larger (although in this proposal, we have not designed the study with the anticipation that we will see effect sizes of this magnitude). We will compute effect sizes from these analyses and regard them as clinically meaningful if they exceed .20 for more distal outcomes and .30 for more proximal outcomes.

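### Section 5.1 does not use the collected baseline score to sharpen the arm comparison, and the 0.70 power in section 5.2 assumes covariates that the planned model does not contain

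*Combined protocol and SAP*

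**What the plan says.** Section 5.1 gives the aim as "To test whether intervention groups differ in their amount of change on treatment outcomes over time". The model has time (four visits, baseline among them), "intervention group, and a group by intervention interaction with random intercepts to account for baseline differences on outcome variables". It lists no covariate, and changes from baseline are to be estimated as least-squares means for each arm.

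The Protocol Synopsis (Statistical and Analytic Plan) describes the same kind of model. It says "Analyses will focus on average change over time (i.e., change from baseline scores) on primary outcomes", and it uses "random intercepts for each subject that will estimate the average change from baseline (i.e., least means change) for each treatment group" at mid-treatment, post-treatment and follow-up. For the biological primary outcome, the Synopsis (Efficacy Evaluations) gives "Least means change from baseline to post-treatment on salivary cortisol". Heart rate variability has the same two visits.

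Section 5.2 takes 20 subjects per group and alpha 0.05, "and covariates that account for 40% of the variance, the study should have reasonable power", with power put at 0.70 for effects of 0.65 or more. The Sample Size Justification in section 2.1 repeats the condition ("covariates that account for 40% of the variance"). Neither place names the covariates. Section 2.2 introduces its list of demographic and clinical items with the words "collected as self-report for possible use as covariates includes", and assigns none of them to a model.

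**The concern.** There are two linked problems.

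**Precision.** A random subject intercept represents differing starting levels and within-subject correlation. It does not adjust the comparison between arms for a chance imbalance at baseline. With baseline as a level of time and free arm means at every visit, the group-by-time contrast is (with complete data) the plain difference in mean change. The baseline score is already collected and could narrow the interval. Section 2.1 gives the goal of the trial as estimating effect sizes for a larger trial, so the width of that interval matters.

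**Power statement.** The 0.70 rests on covariate adjustment that section 5.1 does not contain. A reader cannot tell what power the planned analysis has, or whether the figure is for one visit or for an average over visits.

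**Working it through.** **Inputs from the documents:** 20 per arm, alpha 0.05, effect 0.65, covariates explaining 40% of the variance, stated power 0.70 (sections 2.1 and 5.2).

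**Assumptions:** two-sided test (not stated); complete data; equal SD at every visit, with effects in units of that SD; equal correlation rho between any two visits, as a random-intercept model implies. The documents give no rho, so a range is shown. Power is from the non-central t with 38 df (unadjusted) or 37 df (adjusted).

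**1. The plan's own figure.** The standard error is sqrt(0.6 × 2/20) = 0.245 and power is 0.73. The effect with 0.70 power is 0.62 SD. The stated 0.70 at 0.65 is therefore slightly conservative for the inputs given.

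**2. Variance of the arm contrast, in units of 2/n.**
- One visit: change 2(1 − rho); baseline-adjusted 1 − rho². The ratio adjusted/unadjusted is (1 + rho)/2.
- Average of three post-baseline visits: change (4/3)(1 − rho); adjusted (1 + 2rho)/3 − rho² = (1 − rho)(1 + 3rho)/3. The ratio is (1 + 3rho)/4.

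Both ratios are below 1 for every rho below 1. At rho 0.4, 0.5, 0.632 and 0.8 they are 0.70, 0.75, 0.82 and 0.90 (one visit) and 0.55, 0.63, 0.72 and 0.85 (average).

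**3. Precision at rho 0.5.**
- One visit: the standard error falls from sqrt(1.0 × 0.1) = 0.316 to sqrt(0.75 × 0.1) = 0.274, and the 95% half-width from 0.64 to 0.55 SD.
- Average: the standard error falls from sqrt(0.667 × 0.1) = 0.258 to sqrt(0.417 × 0.1) = 0.204, and the half-width from 0.52 to 0.41 SD.

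**4. Power at 0.65 SD.**

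| rho | One visit, change | One visit, adjusted | Average, change | Average, adjusted |
|---|---|---|---|---|
| 0.4 | 0.45 | 0.59 | 0.61 | 0.86 |
| 0.5 | 0.52 | 0.64 | 0.69 | 0.87 |
| 0.632 | 0.65 | 0.73 | 0.82 | 0.92 |
| 0.8 | 0.89 | 0.92 | 0.97 | 0.99 |

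Unadjusted change reaches 0.70 at rho of about 0.675 for one visit and about 0.51 for the average. Simulation (20,000 trials per setting) agrees. It puts the adjusted columns up to about 0.015 lower, because the formula ignores the cost of estimating the slope.

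**5. Link to section 5.2.** If the covariate behind the 40% is the baseline score, rho = sqrt(0.40) = 0.632. The one-visit adjusted variance is then 1 − 0.40 = 0.60, which gives the 0.73 of step 1. At the same rho, the planned one-visit change contrast has variance 2(1 − 0.632) = 0.735 and power 0.65.

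**6. Which columns apply.** Cortisol and heart rate variability have one post-baseline visit, so only the one-visit columns apply to them. Section 2.1 calls cortisol the primary outcome measure.

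**The case against.** **The interaction term.** A reader might infer that naming an interaction of one factor with itself leaves the efficacy test undefined. The documents do not support that. The aim in section 5.1 and the Synopsis account of change per arm and visit fit only group by time. It is a slip without numerical effect, though it should be corrected.

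**Baseline is already in the model.** This is true: it enters as a response, and unadjusted change is a legitimate, unbiased contrast. With missing visits, likelihood estimation also departs somewhat from the simple difference in change. What remains is the loss of precision.

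**The power figure.** A reader might infer that true power is 0.52 and the detectable effect 0.81 SD, the values with no covariate and no baseline (standard error sqrt(2/20) = 0.316). No part of the plan describes that analysis. The planned contrast has power 0.52 only in the particular case of one visit with rho 0.5. On the visit-averaged reading in the Synopsis, a rho slightly above 0.5 already gives 0.70. Nor is 0.70 overstated for its own inputs, which give 0.73.

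**Little depends on it.** This is a feasibility trial, section 5.2 says effects of 0.65 are not anticipated, and section 2.1 also supports 40 subjects by recruitment. All of that stands, and it limits the point to precision and an accurate power statement. Section 2.2 leaves covariates open, but a list for possible use does not fix a model or support a specific 40%.

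**Conclusion.** The concern holds in a limited form. The planned contrast is valid but gives up precision that the collected baseline could supply: a variance reduction of 25% (one visit) or 37.5% (three-visit average) at an assumed rho of 0.5, and less at higher rho. The power statement in sections 2.1 and 5.2 does not describe the model in section 5.1. Whether the planned contrast falls short of 0.70 cannot be settled from the documents, because it depends on rho and on whether one visit or the average is meant. A shortfall is most plausible for one-visit contrasts, and so for cortisol and heart rate variability, where rho must be about 0.675 or more.

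These figures assume complete data, equal variances and equal correlations. They do not show that 40 subjects is the wrong number. At rho 0.5 every half-width above is wider than the 0.20 and 0.30 benchmarks in section 5.2, with or without adjustment.

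**What to change.** **Section 5.1.** Replace the misnamed interaction and adjust for baseline. One form is:

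> Post-baseline scores are the response. The model includes visit, group, group by visit and the baseline score, with a random subject intercept where an outcome has more than one post-baseline visit. The between-arm difference and its 95% confidence interval are reported at each visit and, where there are several, averaged over visits.

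The alternative keeps baseline as a response and constrains its mean to be equal across arms. Use it only if the sponsor confirms that baseline assessments precede randomisation, which the documents do not state outright. Reporting both the visit-specific and the averaged difference keeps both readings in the Synopsis.

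**Sections 5.2 and 2.1.** Either name the baseline score as the covariate behind the 40%, which implies rho of about 0.63, or restate power for the planned model with an assumed rho. Say whether the figure is for one visit or for the average. If the equal-baseline form is chosen, state the assumption as a correlation so that the sections use the same terms.

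**Cost.** Only wording changes, with no new data or subjects. The restated power may look less favourable than 0.70. In the covariate form, a subject with no post-baseline score contributes nothing to the estimate, and the text on including all randomised subjects should say so. The conflicts over when the DSI and PSS are collected are a separate point.
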